DLT: This section only applies to the Dose Escalation and Cohort Expansion (Part 1) and the SCCHN Cohort Expansion (Part 2), which have both completed enrollment and therefore this section and its subsections are not applicable starting with Amendment 13 and all subsequent amendments or revised protocols. For the purpose of guiding dose escalation, hepatic, non-hematologic, and hematologic DLTs will be defined separately (protocol body [Section 4.8](#)) and will be determined based on the incidence, intensity, and duration of AEs that are related to study drug and that occur within 56 days (8 weeks, through the completion of Cycle 1) of initiation of study drug in the Dose Escalation and Cohort Expansion (Part 1; completed). The severity of AEs will be graded according to the National Cancer Institute (NCI) Common Terminology Criteria for Adverse Events version 4.0 (CTCAE v4.0). For the purposes of subject management, DLTs will lead to dose interruption regardless of the cycle in which a DLT occurs (see protocol body [Section 4.9.3](#) for specific guidelines).

The SCCHN Cohort Expansion (Part 2; Completed): To further explore emerging efficacy and safety data in subjects with SCCHN; an additional cohort of approximately 35 subjects will be treated at Dose Level 4 (see [Table 1](#)). The null hypothesis that the true ORR is 25% will be tested against a 1-sided alternative: ORR = 40%. The null hypothesis will be rejected if 12 or more responses are observed in 35 subjects. This design gives a 1-sided type I error

rate of 0.15 and a power of 0.81. See [Section 1](#) “Clinical Experience with Lirilumab and Nivolumab Combination Treatment” in the protocol body for preliminary safety and efficacy results.

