4.8 Dose Limiting Toxicities

This section only applies to the Dose Escalation and Cohort Expansion (Part 1) and the SCCHN Cohort Expansion (Part 2), which have both completed enrollment and therefore this section and its subsections are not applicable starting with Amendment 13 and all subsequent amendments or revised protocols.

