4.8.3 Definition of Non-hematologic DLT

Any of the following events will be considered a non-hematologic DLT:

- Grade 2 eye pain or reduction in visual acuity that requires systemic treatment
- Grade 2 eye pain or reduction in visual acuity that does not respond to topical therapy and that does not improve to Grade 1 within 2 weeks of initiation of topical therapy
- Grade 3 non-hepatic or non-hematologic toxicity, with the following exceptions:

The following Grade 3 non-hematologic events **will not** be considered DLTs:

- Grade 3 electrolyte abnormality that lasts less than 72 hours, is not clinically complicated, and resolves spontaneously or responds to conventional medical intervention
- Grade 3 increase in amylase or lipase that is not associated with clinical or radiographic evidence of pancreatitis
- Grade 3 nausea or vomiting that lasts less than 48 hours, and resolves to Grade 1 or less, either spontaneously or with conventional medical intervention
- Grade 3 fever that lasts less than 72 hours, and is not associated with hemodynamic compromise (including hypotension, or clinical or laboratory evidence of end organ perfusion impairment)
- Grade 3 endocrinopathy that is well controlled by hormone replacement
- Grade 3 tumor flare (defined as pain, irritation or rash that localizes to sites of known or suspected tumor)
- Grade 3 fatigue
- Grade 3 infusion reaction that returns to Grade 1 in less than 6 hours

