4.9.3 Dose Delays Due To Toxicity

Subjects who experience a DLT must have therapy held. Subjects who are required to permanently discontinue study drug administration are listed in [Section 4.9.5](#). All other subjects will be permitted to resume study drug administration at the same doses for all study drugs following resolution of the AE to Grade 1 or less, or to baseline.

Study drug administration should be delayed for the following:

- Grade 2 non-skin, drug-related AE, with the exception of fatigue
- Grade 2 drug-related creatinine, AST, ALT, and/or total bilirubin abnormalities
- Grade 3 skin, drug-related AE
- Grade 3 drug-related laboratory abnormality, with the following exceptions:
 - Grade 3 lymphopenia or asymptomatic amylase or lipase does not require dose delay
 - Grade ≥ 3 AST, ALT, and total bilirubin will require dose discontinuation (see [Section 4.8](#))
- Any AE, laboratory abnormality, or intercurrent illness, which, in the judgment of the investigator, warrants delaying the dose of study drug

Subjects who require delay of nivolumab should be re-evaluated weekly or more frequently if clinically indicated and resume nivolumab dosing when retreatment criteria are met.

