4.9.5 Guidelines for Permanent Discontinuation

Subjects will be required to permanently discontinue all study drugs for the following AEs:

- 1) Any Grade 2 drug-related uveitis, eye pain, or blurred vision that does not respond to topical therapy and does not improve to Grade 1 severity within the retreatment period OR requires systemic treatment
 - 2) For subjects receiving lirilumab in combination with nivolumab or nivolumab monotherapy (the Dose Escalation and Cohort Expansion [Part 1; completed] and the SCCHN Cohort Expansion [Part 2; completed], the SCCHN Randomized Cohorts [Part 3],): Any Grade 3 non-skin, drug-related AE lasting > 7 days or recurs, with the following exceptions for laboratory abnormalities, drug-related uveitis, pneumonitis, bronchospasm, hypersensitivity reactions, infusion reactions, and endocrinopathies:
 - a) Grade 3 drug-related uveitis, pneumonitis, bronchospasm, hypersensitivity reaction, or infusion reaction of any duration requires discontinuation.
 - b) Grade 3 drug-related endocrinopathies, adequately controlled with only physiologic hormone replacement, do not require discontinuation. Adrenal insufficiency requires discontinuation regardless of control with hormone replacement.
 - c) Grade 3 drug-related laboratory abnormalities do not require treatment discontinuation except:
 - i) Grade 3 drug-related thrombocytopenia > 7 days or associated with bleeding
 - ii) Grade ≥ 3 drug-related AST, ALT, or total bilirubin*
 - iii) Concurrent AST or ALT > $3 \times$ ULN and total bilirubin > $2 \times$ ULN
- * In most cases of Grade 3 AST or ALT elevation, study drug(s) will be permanently discontinued. If the investigator determines a possible favorable benefit/risk ratio that warrants continuation of study drug(s), a discussion between the investigator and the BMS Medical Monitor/designee must occur.
- 3) For subjects receiving lirilumab in combination with nivolumab and ipilimumab (the Signal Detection in SCCHN with Lirilumab, Nivolumab, and Ipilimumab Combination [Part 5]): Any Grade 3 non-skin, drug-related AE lasting > 7 days, or recurs with the following exceptions for laboratory abnormalities, diarrhea, colitis, neurologic toxicity, drug-related uveitis, pneumonitis, bronchospasm, hypersensitivity reactions, infusion reactions, and endocrinopathies:

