 - a) Grade 3 drug-related diarrhea, colitis, neurologic toxicity, uveitis, pneumonitis, bronchospasm, hypersensitivity reaction, or infusion reaction of any duration requires discontinuation.
 - b) Grade 3 drug-related endocrinopathies, adequately controlled with only physiologic hormone replacement, do not require discontinuation. Adrenal insufficiency requires discontinuation regardless of control with hormone replacement.

- c) Grade 3 drug-related laboratory abnormalities do not require treatment discontinuation except:
 - iv) Grade 3 drug-related thrombocytopenia > 7 days or associated with bleeding
 - v) Any drug-related liver function test abnormality that meets the following criteria:
 - (1) Grade ≥ 3 drug-related AST, ALT, or total bilirubin*
 - (2) Concurrent AST or ALT > $3 \times$ ULN and total bilirubin > $2 \times$ ULN

* In most cases of Grade 3 AST or ALT elevation, study drug(s) will be permanently discontinued. If the investigator determines a possible favorable benefit/risk ratio that warrants continuation of study drug(s), a discussion between the investigator and the BMS Medical Monitor/designee must occur.

- 4) Any Grade 4 drug-related AE or laboratory abnormality (including but not limited to creatinine, AST, ALT, or total bilirubin), except for the following events, which do not require discontinuation:
 - a) Isolated Grade 4 electrolyte imbalances/abnormalities that are not associated with clinical sequelae and are corrected with supplementation/appropriate management within 72 hours of their onset
 - b) Grade 4 neutropenia ≤ 7 days
 - c) Grade 4 lymphopenia or leukopenia or asymptomatic amylase or lipase
 - d) Grade 4 lymphopenia < 5 days in duration
 - e) Grade 4 drug-related endocrinopathy AEs, such as hyper- or hypothyroidism, or glucose intolerance, which resolve or are adequately controlled with physiologic hormone replacement (corticosteroids or thyroid hormones) or glucose-controlling agents, respectively, may not require discontinuation after discussion with and approval from the BMS Medical Monitor.
- 5) Any DLT as outlined in [Section 4.8](#) will require permanent discontinuation with the following exceptions:
 - a) Grade 3 diarrhea, nausea, vomiting, or abdominal pain that returns to Grade 1 or baseline within 3 days with medical intervention
 - b) Grade 3 ALT or AST that returns to Grade 1 or baseline within 7 days with medical intervention

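### Protocol Section 4.9.5 item 5 ties permanent discontinuation to the DLT list in Section 4.8, which is declared not applicable, so whether it binds subjects still on treatment is contradictory

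*Protocol*

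**What the plan says.** Section 4.9.5 opens with "Subjects will be required to permanently discontinue all study drugs for the following AEs" and lists seven items. Items 2 and 3 name their Parts (Parts 1, 2 and 3, and Part 5). Item 5 names none: any DLT under Section 4.8 "will require permanent discontinuation with the following exceptions". The exceptions are 5a (certain gastrointestinal events), 5b (ALT or AST) and 5c (pruritus or rash), each with a time limit for recovery.

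Section 4.8 says that it concerns only Parts 1 and 2, whose enrollment is complete, and "therefore this section and its subsections are not applicable starting with Amendment 13 and all subsequent amendments or revised protocols". Section 4.8.1 ties a DLT to the first 56 days on study drug in Part 1.

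Other current text still uses the list:

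- Section 4.9.3 says "Subjects who experience a DLT must have therapy held". It refers to 4.9.5 for those who must stop for good, and lets everyone else restart at unchanged doses once the event is back to Grade 1 or lower, or to baseline. It also cites Section 4.8 for liver values.
- Section 4.9.4 uses the DLT criteria of Section 4.8 to decide on further dosing, and calls Section 4.8 the source of discontinuation limits for combined liver values.
- The Synopsis, in its DLT paragraph, says "DLTs will lead to dose interruption regardless of the cycle in which a DLT occurs". That paragraph carries the same not-applicable statement as Section 4.8.

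**The concern.** A permanent-stop rule is written as current, without limit by Part, but its definitions sit in a section that is switched off. A site must decide for itself whether to use the list.

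Revised Protocol 12 keeps subjects with continuing benefit on study drug, for up to 2 years in all (Overall Rationale; Section 1.5), so the rule is not merely historical. Two sites could handle the same event differently, one stopping for good and the other resuming. That bears first on the safety and treatment of individual subjects. It also bears on exposure and on adverse events leading to discontinuation, which SAP Section 4.1 lists among the safety measures.

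**Working it through.** No sample size, power or error rate depends on this point. The check sets the passages side by side.

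**Definitions used**

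- 4.8.3 counts as a DLT any related "Grade 3 non-hepatic or non-hematologic toxicity, with the following exceptions". Arthralgia and general rash are not among the exceptions. A Grade 3 electrolyte abnormality is excepted only if it lasts under 72 hours, is uncomplicated, and resolves or responds to treatment.
- 4.8.4 counts Grade 4 neutropenia of more than 5 days.
- Item 2 is triggered by "Any Grade 3 non-skin, drug-related AE lasting" more than 7 days, or by recurrence. Item 3 sets the same trigger for Part 5.
- Items 2c and 3c say that Grade 3 related laboratory abnormalities, apart from listed platelet and liver criteria, need no discontinuation. Item 4b says the same of Grade 4 neutropenia of up to 7 days.

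**Outcome under each reading**, assuming that items 6 and 7 (long delay; investigator's judgment) are not triggered:

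| Related event | Section 4.8 list used | Section 4.8 void |
|---|---|---|
| First Grade 3 arthralgia, 4 days | DLT, outside 5a to 5c: permanent stop | 4 ≤ 7 days and not recurrent, so items 2 and 3 are not met; 4.9.3 permits resumption after resolution |
| Grade 3 rash, 10 days | DLT; 10 > 7 days, so 5c does not apply: permanent stop | Items 2 and 3 cover non-skin events only; 4.9.3 delays dosing, and 4.9.3 and 4.9.4 permit resumption after resolution |
| Grade 3 electrolyte abnormality, 72 hours or more | DLT, so item 5 stops; items 2c and 3c say no discontinuation is needed | Items 2c and 3c alone: no required stop |
| Grade 4 neutropenia, more than 5 and up to 7 days | DLT, so item 5 stops; item 4b says no discontinuation is needed | Item 4b alone: no required stop |

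In the first two rows each reading gives one outcome, and the two outcomes are opposite. In the last two rows, using the list also sets item 5 against another item of the same section.

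**Section 4.8 taken with its own time window.** If 4.8.1 is applied in full, no Part 3 or Part 5 event is a DLT. Part 1 had completed enrollment by Amendment 13 (12-Dec-2016), and Revised Protocol 12 is dated 08-May-2018: 365 + 147 = 512 days later. Allowing 28 days of screening, 512 − 28 = 484 days, well past 56. On this reading item 5 catches nobody in Part 1 who is still on drug either. Item 5 has force for current subjects only if the list is borrowed without its stated scope and window, and nothing in 4.9.5 says whether that is meant.

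**The case against.** The strongest reply is that Section 4.8 settles the matter: it is not applicable, so item 5 is empty and the remaining items govern. On that reading there is a dead cross-reference and no double instruction. This is a fair reading, but the text does not establish it. Sections 4.9.3 and 4.9.4 go on using DLTs and Section 4.8 for current dosing, and item 5 was left in a list whose lead-in has no limit by Part. For combined liver values the choice matters little, because items 2c and 3c repeat the criterion of ALT or AST above 3 × ULN with bilirubin above 2 × ULN.

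A second reply is that 4.9.5 lists stop triggers, so failing to meet item 2 or 3 is not permission to continue. That is right as far as those items go. The permission comes from 4.9.3, which lets anyone not listed in 4.9.5 restart after resolution. It could also be said that 2c, 3c and 4b sit inside their own items and do not limit item 5. They are nonetheless worded as statements that no discontinuation is required, so a site has textual support either way.

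Third, the Synopsis wording on interruption need not contradict item 5. A hold followed by a decision under 4.9.5 is a sequence, and no weight is placed on it here.

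Three stronger inferences are tempting, and the documents do not support them:

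- *That a subject is stopped and kept on drug at once.* For arthralgia and rash the two outcomes belong to alternative readings. Nor is every DLT a stop, because 5a to 5c are excepted.
- *That Part 5 diarrhea is a further conflict.* Exception 5a covers "Grade 3 diarrhea, nausea, vomiting, or abdominal pain that returns to Grade 1 or baseline within 3 days with medical intervention", while 3a stops Part 5 subjects for Grade 3 diarrhea of any duration. But 5a exempts only from item 5, so 3a still applies and the outcome is the same under either reading.
- *That 36 of 322 subjects (11.2%) are exposed.* That figure (Protocol Section 1) counts all related Grade 3 or 4 events. Of the types named there, Grade 3 lipase or amylase increases without pancreatitis are not DLTs, and Grade 3 AST increases and infusion reactions already fall under item 2, AST subject to its footnote.

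**Conclusion.** The contradiction is real and must be reconciled. A permanent-stop rule without limit by Part depends on definitions that the protocol declares not applicable, while neighboring sections still use them.

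Its size can be shown by type of event but not by count. At least two kinds of event have opposite outcomes depending on the reading, and two more set item 5 against another item of 4.9.5 if the list is used. The number of subjects affected cannot be derived from the documents.

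The problem is not confined to Parts 3 and 5, since item 2 also governs Parts 1 and 2. The effect on reported results is limited: under SAP Sections 7.1 and 7.6, adverse-event summary tables pool Parts 1 and 2, and Parts 3 and 5 appear in listings only. The main stake is consistent and safe handling of subjects still on drug.

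This conclusion assumes that the events are drug-related and that items 6 and 7 do not apply. It takes no view on which clinical outcome is right.

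**What to change.** State for which Parts and cycles item 5 of Section 4.9.5, and the DLT and Section 4.8 references in 4.9.3 and 4.9.4, are in force. Then reconcile item 5 with items 2, 3 and 4b so that each event has one outcome. The four events in the table can serve as test cases for the revised text. Which outcome applies is for the sponsor's medical team to decide.

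The cost is a wording change in Section 4.9, communicated to sites. No assessments, visits or data collection are added.

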5 STUDY ASSESSMENTS AND PROCEDURES

5.1 Flow Chart/Time and Events Schedule

5.1.1 *Dose Escalation and Dose Expansion (Part 1; Completed) and the SCCHN Cohort Expansion (Part 2; Completed)*

Table 5.1.1-1: Screening Procedural Outline the Dose Escalation and Dose Expansion (Part 1; Completed) and the SCCHN Cohort Expansion (Part 2; Completed) (CA223001)

Procedure	Screening Visit (D -28 to -1)	D -14 to -1	D -3 to -1 Visit	Notes
Eligibility Assessments				
Informed Consent	X			A subject is considered enrolled only when a protocol-specific informed consent is signed.
Inclusion/Exclusion Criteria	X			
Medical History	X			May include more detailed medical history of risk factors for potential events such as pulmonary related events.
Archived tumor tissue samples	X			One paraffin block or 5 to 15 FFPE unstained slides identified prior to enrollment/randomization. For the SCCHN Cohort Expansion (Part 2), confirmation of tumor tissue receipt at central laboratory is required before subjects receive study drug.
Safety Assessments				
Physical Examination	X			If the screening PE is performed within 24 hours of dosing on Cycle 1 Day 1 then a single exam may count as both the screening and pre-dose evaluation.
Performance Status	X			ECOG Performance Status (see Appendix 7).
Physical Measurements	X			Includes height, weight.
Vital Signs	X			Includes body temperature, seated blood pressure, and heart rate. Blood pressure and heart rate should be measured after the subject has been seated quietly for at least 5 minutes.
Oxygen Saturation			X ^a	Collected at rest. Oxygen levels will be used in combination with clinical signs and symptoms and radiographic images to evaluate

Table 5.1.1-1: Screening Procedural Outline the Dose Escalation and Dose Expansion (Part 1; Completed) and the SCCHN Cohort Expansion (Part 2; Completed) (CA223001)

Procedure	Screening Visit (D -28 to -1)	D -14 to -1	D -3 to -1 Visit	Notes
				pulmonary/respiratory status. Changes in oxygen levels will not be used in isolation to document or diagnose pulmonary toxicity.
Electrocardiogram	X			12-lead ECG.
Chest Radiograph	X			
Laboratory Tests		X		Day -14 to -1 prior to Cycle 1 Day 1. To include: CBC with differential, LFTs (to include a minimum of AST, ALT, alkaline phosphatase, total bilirubin, and LDH), BUN, creatinine, Ca, Mg, Na, K, carbon dioxide, Cl, phosphorous, glucose, albumin, amylase, lipase, CRP, TSH with reflex (free T3 and free T4), hepatitis B/C, and HIV testing (Subjects with HCC only, PT, PTT, INR, and fibrinogen) If performed within 72 hours of dosing on Cycle 1 Day 1, then Cycle 1 Day 1 laboratories are not required.
HPV Status	X			The Dose Escalation and Dose Cohort (Part 1): SCCHN subjects only. Sites must submit and document prior HPV status and subtype, particularly HPV16 and HPV18 (p16 immunohistochemistry positive or negative status is recommended). The SCCHN Cohort Expansion (Part 2) Sites must submit prior HPV status if known. For subjects with unknown status, tumor tissue will be required, per inclusion criteria. Subjects must consent to HPV testing.
MSI Status	X			CRC subjects only. Sites must submit and document prior MSI testing and results. If MSI status is known prior to study entry, repeat testing will not be required during the screening period, but tissue must be available for repeat MSI testing if requested.
Child-Pugh Score	X			HCC subjects only. See Appendix 5
Serum Pregnancy Test			X ^a	

Table 5.1.1-1: Screening Procedural Outline the Dose Escalation and Dose Expansion (Part 1; Completed) and the SCCHN Cohort Expansion (Part 2; Completed) (CA223001)

Procedure	Screening Visit (D -28 to -1)	D -14 to -1	D -3 to -1 Visit	Notes
Concomitant Medication		X		Collected for the period 2 weeks prior to Cycle 1 Day 1. (Note: Immunosuppressive medications are recorded on a separate log page.)
Assessment of Signs and Symptoms		X		Collected for the period 2 weeks prior to Cycle 1 Day 1.
Adverse Event Reporting				
Monitor for Serious Adverse Events	X			All SAEs must be collected starting at the time the subject signs informed consent and through 150 days after discontinuation of dosing. SAEs should be approved in TAO within 4 days of entry
Efficacy Assessments				
Diagnostic Imaging	X			CT with contrast is the preferred modality (MRI if CT is not feasible). Assessment should include the chest/abdomen/pelvis at a minimum; and should include other anatomic regions as indicated by individual subject disease histories.
Brain Imaging	X			Brain imaging (CT/MRI) for subjects with history or symptoms of brain metastases or who have not had brain imaging within 30 days of anticipated first study drug administration.
Bone Scan	X			As clinical indicated (ie, subjects with history or symptoms of bone metastases), but bone scans will not be considered a modality for assessment for measurable disease.
Serologic Tumor Markers	X			To include measuring for tumor types with known serologic markers (ie, CEA for subjects with CRC, PSA for subjects with prostate ca, CA-125 for subjects with ovarian/breast cancer, alpha fetoprotein for subjects with HCC, hepatitis B DNA PCR for subjects with hepatitis B, and hepatitis C RNA PCR for subjects with hepatitis C, etc). To be collected prior to the first dose of study drug.

Table 5.1.1-1: Screening Procedural Outline the Dose Escalation and Dose Expansion (Part 1; Completed) and the SCCHN Cohort Expansion (Part 2; Completed) (CA223001)

Procedure	Screening Visit (D -28 to -1)	D -14 to -1	D -3 to -1 Visit	Notes
Clinical Drug Supplies				
Subject Registration			X	

^a May be obtained on Cycle 1 Day 1 with results evaluated prior to study drug administration.

BUN = blood urea nitrogen; Ca = calcium; CEA = carcinoembryonic antigen; CBC = complete blood count; Cl = chloride; CRP = C-reactive protein; D = Day; ECG = electrocardiogram; INR = international normalized ratio; K = potassium; LDH = lactate dehydrogenase; LFT = liver function test; Mg = magnesium; Na = sodium; PE = physical examination; PSA = prostate-specific antigen; PT = prothrombin time; PTT = partial thromboplastin time; T3 = triiodothyronine; T4 = thyroxine; TAO = Trial Access Online; TSH = thyroid-stimulating hormone.

Table 5.1.1-2: On-treatment Procedural Outline the Dose Escalation and Dose Expansion (Part 1; Completed) and the SCCHN Cohort Expansion (Part 2; Completed) (CA223001)

Procedure	Cycles 1 to 12					Notes
	D1 (± 2 days)	D15 (± 2 days)	D29 (± 2 days)	D43 (± 2 days)	D49 to 56	
Safety Assessments						
Physical Examination	X					A symptom directed physical examination performed by the investigator or designee is required at each subsequent visit.
Performance Status	X	X	X	X		ECOG score (see Appendix 7)
Physical Measurements	X	X	X	X		Weight only.
Vital Signs	X	X	X	X		
Vital signs will be obtained before the nivolumab infusion, after the nivolumab infusion, and after the lirilumab infusion.
 
If any vital sign is abnormal at the final check, the subject must be observed further for a period of time, as clinically indicated.
 
The start and stop time of the study drug infusion should be documented. If there are any new or worsening clinically significant changes since the last examination, report changes on the appropriate non-serious or serious adverse event page.
 
When slowing or restarting an infusion due to an infusion reaction, vital signs should be monitored every 15 minutes (± 5 minutes) or as directed by the investigator until the infusion is completed and/or the subject is stabilized. If a subject has an infusion reaction with nivolumab, the lirilumab infusion can be given (without prophylactic medications) if the infusion reaction resolves within 3 hours. For scheduling purposes after a nivolumab infusion reaction, the lirilumab infusion may be given the next day. Prophylactic pre-infusion medications should be given prior to all subsequent nivolumab infusions.

Electrocardiogram	X					
12-lead ECG (if performed on same day as study drug administration it is to be performed prior to dosing).
 
Not required on Cycle 1 Day 1

Table 5.1.1-2: On-treatment Procedural Outline the Dose Escalation and Dose Expansion (Part 1; Completed) and the SCCHN Cohort Expansion (Part 2; Completed) (CA223001)

Procedure	Cycles 1 to 12					Notes
	D1 (± 2 days)	D15 (± 2 days)	D29 (± 2 days)	D43 (± 2 days)	D49 to 56	
Chest Radiograph						As clinically indicated.
Oxygen Saturation Levels	X	X	X	X		Collected at rest prior to dosing.
Laboratory Tests	X	X	X	X		On-study laboratory tests (including pregnancy testing) to be done on site/local. Within 72 hours of re-dosing to include CBC with differential, LFTs (to include a minimum of AST, ALT, alkaline phosphatase, total bilirubin, and LDH), BUN, creatinine, glucose, Ca, Mg, Na, K, carbon dioxide, Cl, phosphorous, amylase, and lipase. Results should be examined by the investigator or appropriate designee prior to dose administration. (Subjects with HCC only, PT, PTT, INR, and fibrinogen) CBC with differential should also be collected at each timepoint where samples for immunophenotyping are collected as listed in Table 5.7.3.3-1 , Table 5.7.3.3-3 , and Table 5.7.3.3-4 .
Child-Pugh Score	X					HCC only.
Endocrine Panel	X					To include TSH with reflex testing (free T3 and free T4). Results should be examined by the investigator or appropriate designee within 48 hours of dose administration.
Pregnancy Test	X	X	X	X		Serum or urine.
Adverse Event Reporting						
Monitor for Non-serious Adverse Events	X	X	X	X		Non-serious AEs will be collected starting with the first dose of study drug and through 150 days after discontinuation of dosing or until the start of subsequent anti-cancer therapy.
Monitor for Serious Adverse Events	X	X	X	X		All SAEs must be collected starting at the time a subject signs informed consent and through 150 days after discontinuation

Table 5.1.1-2: On-treatment Procedural Outline the Dose Escalation and Dose Expansion (Part 1; Completed) and the SCCHN Cohort Expansion (Part 2; Completed) (CA223001)

Procedure	Cycles 1 to 12					Notes
	D1 (± 2 days)	D15 (± 2 days)	D29 (± 2 days)	D43 (± 2 days)	D49 to 56	
						of dosing. SAEs should be approved in TAO within 4 days of entry
Sample Collection						
PK Assessments						See Table 5.7.3.3-1 , Table 5.7.3.3-2 , Table 5.7.3.3-3 , and Table 5.7.3.3-4 . To be collected on Days 1, 2, 8, 15, 29, 85, 86, 92, and 113.
Immunogenicity Assessments						See Table 5.7.3.3-1 , Table 5.7.3.3-2 , Table 5.7.3.3-3 , and Table 5.7.3.3-4 . To be collected on Days 1, 2, 8, 15, 29, 85, 86, 92, and 113
Biomarker Assessments						See Table 5.7.3.3-1 , Table 5.7.3.3-2 , Table 5.7.3.3-3 , and Table 5.7.3.3-4 . To be collected on Days 1, 2, 8, 15, 29, 85, 86, 92, and 113. Subjects in Cohort Expansion (Part 1) with MEL and SCCHN must utilize Table 5.7.3.3-3 .
Efficacy Assessments						
Diagnostic Imaging					X	By methods used at baseline. Scans will be performed Q8W relative to the Cycle 1 Day 1 visit regardless of treatment delays.
Brain Imaging					X	As clinically indicated.
Bone Scan					X	As clinically indicated.
Serologic Tumor Markers					X	To include measuring for tumor types with known serologic markers (ie, CEA for subjects with CRC, PSA for subjects with prostate ca, CA-125 for subjects with ovarian/breast cancer, alpha fetoprotein for subjects with HCC, hepatitis B DNA PCR for subjects with hepatitis B, and hepatitis C RNA PCR for subjects with hepatitis C, etc).

Table 5.1.1-2: On-treatment Procedural Outline the Dose Escalation and Dose Expansion (Part 1; Completed) and the SCCHN Cohort Expansion (Part 2; Completed) (CA223001)

Procedure	Cycles 1 to 12					Notes
	D1 (± 2 days)	D15 (± 2 days)	D29 (± 2 days)	D43 (± 2 days)	D49 to 56	
Clinical Drug Supplies						
Nivolumab Administration	X	X	X	X		
Lirilumab Administration	X		X			To be administered 30 minutes after completion of the nivolumab infusion.

BUN = blood urea nitrogen; Ca = calcium; CEA = carcinoembryonic antigen; CBC = complete blood count; Cl = chloride; D = Day; ECG = electrocardiogram; INR = international normalized ratio; K = potassium; LDH = lactate dehydrogenase; LFT = liver function test; Mg = magnesium; Na = sodium; PSA = prostate-specific antigen; PT = prothrombin time; PTT = partial thromboplastin time; Q8W = every 8 weeks; T3 = triiodothyronine; T4 = thyroxine; TAO = Trial Access Online; TSH = thyroid-stimulating hormone.

Table 5.1.1-3: Follow-up Procedural Outline the Dose Escalation and Dose Expansion (Part 1; Completed) and the SCCHN Cohort Expansion (Part 2; Completed) (CA223001)

Procedure	Clinical Follow-up				Survival Follow-up	Notes
	1 30 days (± 5 days)	2 60 days (± 5 days)	3 100 days (± 5 days)	4 150 days ^a (± 5 days)	Q12W (± 2 weeks)	
Safety Assessments						
Physical Examination	X	X	X			
Vital Signs	X	X	X			Includes body temperature, seated blood pressure, and heart rate. Blood pressure and heart rate should be measured after the subject has been seated quietly for at least 5 minutes.
Performance Status	X	X	X			ECOG score (see Appendix 7)
Laboratory Tests			X			CBC with differential, LFTs (to include a minimum of AST, ALT, alkaline phosphatase, total bilirubin, and LDH), BUN, creatinine, glucose, Ca, Mg, Na, K, carbon dioxide, Cl, phosphorous, amylase, and lipase.
Child-Pugh Score			X			HCC subjects only
Adverse Event Reporting						
Monitor for Non-serious Adverse Events	X	X	X	X		Non-serious AEs will be collected starting with the first dose of study drug and through 150 days after discontinuation of dosing or until the start of subsequent anti-cancer therapy.
Monitor for Serious Adverse Events	X	X	X	X		All SAEs must be collected starting at the time a subject signs informed consent and through 150 days after discontinuation of

Table 5.1.1-3: Follow-up Procedural Outline the Dose Escalation and Dose Expansion (Part 1; Completed) and the SCCHN Cohort Expansion (Part 2; Completed) (CA223001)

Procedure	Clinical Follow-up				Survival Follow-up	Notes
	1 30 days (± 5 days)	2 60 days (± 5 days)	3 100 days (± 5 days)	4 150 days ^a (± 5 days)	Q12W (± 2 weeks)	
						dosing. SAEs should be approved in TAO within 4 days of entry.
Sample Collection						
PK Assessments	X	X	X			See Table 5.7.3.3-1, Table 5.7.3.3-2, Table 5.7.3.3-3, and Table 5.7.3.3-4.
Immunogenicity (ADA) Assessments	X	X	X			See Table 5.7.3.3-1, Table 5.7.3.3-2, Table 5.7.3.3-3, and Table 5.7.3.3-4
Efficacy Assessments						
Diagnostic Imaging			X		X	By method used at baseline. At the end of the clinical follow-up period, non-progressive subjects will continue to have scans Q12W for up to 1 year and then at a minimum of every 6 months thereafter until PD. Imaging to include brain or bone imaging as clinically indicated.

Table 5.1.1-3: Follow-up Procedural Outline the Dose Escalation and Dose Expansion (Part 1; Completed) and the SCCHN Cohort Expansion (Part 2; Completed) (CA223001)

Procedure	Clinical Follow-up				Survival Follow-up	Notes
	1 30 days (± 5 days)	2 60 days (± 5 days)	3 100 days (± 5 days)	4 150 days ^a (± 5 days)	Q12W (± 2 weeks)	
Survival Status						
Assessment Subject Survival Status ^b					X	Subject status will be assessed by either a clinic visit or telephone contact Q12W (± 2 weeks) for up to 3 years following the first dose of study drug. The nature and start dates of any new therapies during this period will be recorded.

^a 150-day follow-up may be performed via clinic visit or telephone contact.

^b No longer required with Revised Protocol 12.

BUN = blood urea nitrogen; Ca = calcium; CBC = complete blood count; Cl = chloride; K = potassium; LDH = lactate dehydrogenase; LFT = liver function test; Mg = magnesium; Na = sodium; TAO = Trial Access Online.

